##### 5.12.1. Extent of Drug Exposure and Compliance

For subjects randomized under protocol version 5.0 or above, it was planned that a subject receives four tablets (2 tablets twice) orally per day for 52 weeks:

- 16 mg/day: 4 mg four times per day

Sponsor:	TauRx Therapeutics Ltd.		
Protocol:	TRx-237-039		
Document Version No.:	3.0	Document Date:	07-JUN-2023

- 8 mg/day: 4 mg twice and control twice per day
- Control: Control four times per day (with one MTC 4 mg tablet interspersed on two occasions within each week on a deterministic but variable schedule allowing one to five days between two doses)

For subjects randomized in version 2.1, it was planned that a subject receives two tablets orally per day for 6 months. If such a subject reconsented to version 3.0 or higher, they subsequently received four tablets orally per day.

First dose dates, dose interruptions, and last dose dates are documented in the eCRFs.

Drug accountability: the record of all study drug dispensed to and returned by subjects (including kit ID and a comment field) is recorded in the RTSM system. The drug accountability information is shared as an SAS file. Things to note are:

- Total Dispensed is auto populated by the system and is dependent on the kit type. Protocol versions v1-v3 have 210 tablets and protocol versions v4+ have 420 tablets.
- Total Used Qty, Total Unused Qty, Total Lost Qty & Total Damaged Qty along with the Accountability Comments are entered by the site. Any queries with the data in these columns should be directed to the person in column Accounted By or Verified By.
- There will be at least two rows per kit when accountability has been verified. Column Action Taken will be populated with an "I" or "U" where "I" is the initial entry and "U" is an updated/verification entry.
- The report only lists kits that have had drug accountability performed in Trident. If the site has not performed drug accountability in Trident, then the kit will not appear in the report.
- Baseline, Week 13, Week 26, and Week 39 visits are performed during double-blind treatment phase where one kit is dispensed at each visit. Week 52 (OL) and Week 78 (OL) are performed during the open-label treatment phase where two kits are dispensed.

The drug accountability sheet therefore has several rows for one dispensed visit/kit. It monitors the initial creation and every update done to it. To analyze the data, the most recent information will be used, which is the last entry, by using the sorting of the raw data file, of each kit.

The following information will be summarized descriptively by treatment group and overall, whereas subjects randomized to placebo/control will be analyzed separately by subjects receiving only true placebo and subjects receiving at least one dose of MTC:

- Total duration of exposure (in weeks): (last dose date – first dose date + 1)/7
- Total duration of treatment (in weeks), which excludes days in which dose was interrupted
- Mean daily dose: Total of administered dose during the duration of exposure, relative to the total duration of exposure

Sponsor:	TauRx Therapeutics Ltd.		
Protocol:	TRx-237-039		
Document Version No.:	3.0	Document Date:	07-JUN-2023

- Total subject-years of exposure: sum of total exposure in years

$$\frac{1}{365.25} \sum_{\text{subjects}} \frac{\# \text{tablets taken during db phase}}{\# \text{tablets planned during db phase}} * \text{total duration of exposure (days)}$$

- Compliance: # Tablets taken / # tablets planned until Week 52 (or until early study drug termination). Including frequency and percentage of subjects with <80% and >120% compliance. A compliance flag will be re-calculated together with the actual compliance figure.
- Frequency and percentage of subjects with dose interruptions
- Frequency and percentage of subjects in the duration of exposure categories (with categories based on the scheduled day for each planned visit, see Table 5: 1 day, 2 to 29 days, 30 to 92 days, etc.), based on total duration of exposure, including interruption days

This summarization will be done for the Safety population, but also repeated restricted to the subjects randomized before protocol version 5.0, and restricted to the subjects randomized under or after protocol version 5.0 (Safetyv5).

Subject data listings will encompass dosing, drug accountability, and compliance. Any doses that are other than that randomized will be flagged and the protocol version under which the subject had been randomized will be given.

#### 5.12.2. Adverse Events

Adverse events (AEs) will be coded using the MedDRA version 20.1 and are displayed in tables and listings using SOC and PT.

Treatment emergent AEs (TEAE) are defined as AEs with:

- Onset after first dose of study drug or
- Worsen in intensity after first dose of study drug or
- Worsen in treatment relationship after first dose of study drug

Based on the Safety population, a time-to-event analysis (event: any TEAE) will be performed using the model as described in Section 5.9.5). The time-to-first TEAE will be calculated as date of onset – date of first dose + 1, and subjects with no TEAE will be censored at the time of study discontinuation.

AEs are summarized by subject incidence rates, therefore, in any tabulation, a subject contributes only once to the count for a given AE (SOC or PT, most related occurrence, or most intense occurrence) regardless the number of episodes.

The total number of subjects and the numbers stratified by MedDRA SOC and PT, along with the corresponding percentage, with the following AE will be derived and summarized by treatment group and overall:

Sponsor:	TauRx Therapeutics Ltd.		
Protocol:	TRx-237-039		
Document Version No.:	3.0	Document Date:	07-JUN-2023

- Any TEAE (separate columns for true placebo and MTC)
- Any TEAE with an onset of Day 1 (separate columns for true placebo and MTC), complemented by a subject data listing
- Any TEAE (categorized by severity, and separate columns for true placebo and MTC), repeated for the Safetyv5 population.
- Any TEAE (categorized by severity) which occurred within two weeks after any COVID-19 vaccination (separate columns for true placebo and MTC)
- Any TEAEs assessed by the Investigator as related to treatment (i.e., related or possibly related) (separate columns for true placebo and MTC)
- Any TEAEs severe in intensity and assessed by the Investigator as related to treatment (as defined above) (separate columns for true placebo and MTC)
- Any TEAE that resulted in interruption or discontinuation of study drug (presented separately and combined) (separate columns for true placebo and MTC)
- Any SAE (separate columns for true placebo and MTC)
- Any serious adverse reaction (SAR), which are the SAEs judged to be possibly related or related to the study drug by the Investigator (separate columns for true placebo and MTC)
- Malignancies other than non-melanoma skin cancers (separate columns for true placebo and MTC)
- COVID-19 infection, a Pearson's chi-square test is used to compare the frequencies pairwise versus the control group
- *TauRx AE Groupings:* Subsets of TEAEs (defined by PT, the latest version of this allocation list, which is to be used in the analysis, was provided to Cytel prior to the database lock of the double-blind treatment phase), summarized per grouping and sub-grouping (separate columns for true placebo and MTC), repeated for the Safetyv5 population
  - Group: Targeted Gastrointestinal Events
    - Sub-group: Diarrhea
    - Sub-group: Gastrointestinal Irritation
    - Sub-group: Nausea/Vomiting
  - Group: Renal and Urinary Disorders (Including Infections)
    - Sub-group: Urinary Tract Infection
    - Sub-group: Urinary Frequency/Urgency

Sponsor:	TauRx Therapeutics Ltd.		
Protocol:	TRx-237-039		
Document Version No.:	3.0	Document Date:	07-JUN-2023

- Group: Anemia and Related Terms
  - Subgroup: Anemia (excluding vitamin deficiencies)
- Group: Falls and Related Terms
  - Sub-group: Falls
- Group: Hypersensitivity
  - Sub-group: Rash
- Group: Renal Function Impairment
- Group: Hepatic Function Impairment
- Group: Behavioral and Psychological Symptoms of Dementia
  - Sub-group: Affective/Anxiety Symptoms
  - Sub-group: Behavioral Symptoms
  - Sub-group Psychotic Symptoms
  - Sub-group: Sleep Disorders
- Group: Cardiac Ischemia
- TauRx AE Groupings will be repeated for the following subgroups, showing only the main *TauRx AE Groupings*:
  - AChEI/memantine use (prior use, never used) [binary], repeated for
    - Discontinuation of AChEI and/or memantine before entering the study
    - Discontinuation of AChEI and/or memantine for purposes of study participation
  - Age group (<75 years, ≥75 years) [binary]
  - Sex (male, female) [binary]
  - Race (White, non-White) [binary], Race = White (if only race checked), otherwise Race = non-White (even if multiple races, including White, were checked)
  - Renal Function at Baseline: Creatinine Clearance (≤ 50 mL/min, > 50 mL/min) [binary]
  - Use or no use of concomitant medications with serotonergic potential (see latest version of the Serotonergic Drugs List, Section 5.8) at any time during the study [binary]
  - Use or no use of SSRI/SNRI [binary]
  - Use or no use of MAOI [binary]

Sponsor:	TauRx Therapeutics Ltd.		
Protocol:	TRx-237-039		
Document Version No.:	3.0	Document Date:	07-JUN-2023

---

- The protocol-specified AEs of special interest (AESI), which are hemolytic anemia and lens discoloration (separate columns for true placebo and MTC). A list of all identified events will be provided to the Statistical Programming team.
- On-study TEAEs of subjects who withdrew from AChEI/memantine for purposes of the study (separate columns for true placebo and MTC)

No formal hypothesis-testing analysis of AEs incidence rates will be performed.

All AEs occurring on study will be listed in a subject data listing. Pre-treatment AEs (onset after informed consent and prior to the first dose of study drug) and post-treatment TEAEs (subset of TEAEs with an onset or worsen in intensity or treatment attribution more than 14 days after last dose of study drug) will be flagged. In addition, separate summaries of AEs by MedDRA SOC and PT will be provided for:

- Pre-treatment AEs
- Pre-treatment AEs of subjects who withdrew from AChEI/memantine for purposes of the study
- Post-treatment TEAEs (separate columns for true placebo and MTC)

Furthermore, subject data listings will be provided for the following: AEs leading to dose interruptions, SAEs (separate for fatal and non-fatal), SARs, AEs leading to withdrawal, and malignancies other than non-melanoma skin cancers.

A subject data listing will be provided, which presents additional SAE information.

#### 5.12.3. Laboratory Data

Central laboratory data are transferred electronically by Labcorp (previously known as Covance). The Data Transfer Specification document provides a detailed description of the content and format of the laboratory datasets.

Clinical laboratory values will be reported in separate tables and listings for conventional and SI units, justified by the involvement of FDA and EMA.

The Baseline value is defined as the last non-missing value prior to first dose of study drug. Laboratory tests obtained on the date of the first dose will be assigned to pre-treatment; the relative times of blood sampling and dosing will be checked programmatically to confirm this assumption, if this is not true, the respective Screening value will be used.

The Baseline value, the actual value and change from Baseline to each on study evaluation and to the last available on-treatment value will be summarized for each clinical laboratory parameter, including hematology, and blood chemistry; restricted to subjects with at least one post-Baseline value. For continuous laboratory parameters n, Mean, Median, SD and (Min, Max) will be presented; and counts and percentages for categorical parameters. In the event of repeated values, the “worst” value per

Sponsor:	TauRx Therapeutics Ltd.		
Protocol:	TRx-237-039		
Document Version No.:	3.0	Document Date:	07-JUN-2023

study day will be used. For the hematology parameters hemoglobin and hematocrit, this descriptive analysis will be prepared separately for males and females.

Visit windows are used when results are presented by target visit (see Table 5). For each parameter, if a subject has multiple values within a visit window, the “worst” value will be used for that visit window summary (see Appendix 12.3).

Shift tables will be provided showing the change from Baseline relative to the reference range. Missing categories will be included in the shift tables.

Box-and-whisker plots and line graphs (showing the mean and standard error) of the observed data will be presented for selected parameters including hemoglobin (separately for males and females), reticulocytes, neutrophils, platelet counts, and liver function tests (ALT, AST, GGT, total bilirubin). Conventional and SI units will both be presented within each figure (as two y-axes), along with reference lines for the normal ranges. Other parameters may be identified during data review.

The treatmentwise correlation (HMTM 16 mg/day, HMTM 8 mg/day, and control) between the G6PD value at Screening and the change in hemoglobin from Baseline up to Week 52 visit will be analyzed. Separate scatter plots will present the values of G6PD and hemoglobin, along with the treatmentwise p-values based on the parametric Pearson correlation. If the Week 52 visit value is not available, the last available on-treatment value will be used. In addition, the change in hemoglobin from Baseline up to Week 52 visit will be analyzed using an ANCOVA, including the randomization stratification variables (see Section 2.6) as fixed factors, the hemoglobin Baseline value and the total duration of exposure (see Section 5.12.1) as covariates, and the treatment indicator; with the Kenward and Roger method used for calculating the denominator degrees of freedom for the tests of fixed effects. This will be performed in two G6PD subgroups: one subgroup includes all subjects with a G6PD Screening value between 60 and 80 percent relative to the lower bound of the laboratory’s reference range, and one subgroup includes all subjects with a G6PD Screening value higher than 80 percent relative to the lower bound of the laboratory’s reference range.

All laboratory data (hematology, and blood chemistry) will be provided in subject data listings, including flags for values outside the reference range, as well as for values being potentially clinically significant (PCS, see Table 6), and for value obtained at a local laboratory. When there are thresholds provided for low and high values, they will be handled separately. A listing will also be provided that details the normal ranges from the central laboratory for all parameters in this study.

Sponsor:	TauRx Therapeutics Ltd.		
Protocol:	TRx-237-039		
Document Version No.:	3.0	Document Date:	07-JUN-2023

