### ***8.1.2 Nonclinical Data***

In cell models, LMT (including as LMTM) has been shown to prevent aggregation and facilitate disaggregation of pre-existing oligomers and fibers. In transgenic mouse models, facilitation of clearance of tau aggregates and associated improvements in cognitive and motor learning abilities have been demonstrated. Tau pathology in these transgenic mouse models has been shown to be ameliorated in certain brain regions (*e.g.*, entorhinal cortex, hippocampus, and neocortex) following treatment with LMTM.

The primary toxicity of MT is hematological, manifesting as methemoglobinemia and a regenerative hemolytic anemia. Depending on the species, Heinz body formation also occurs. A no-observed-adverse effect-level (NOAEL) of 3 to 5 mg MT/kg/day was established in rats, regardless of salt or duration, depending on the low dose in a given study; the parent

MT/LMT plasma levels (exposure) at these doses are comparable to human exposure at an LMTM dose of 8 mg/day. In monkeys, the NOAEL for hematological toxicity was 0.9 mg MT/kg/day in the 6-month MTC phase (toxicokinetic data at this dose are not available); the NOAEL in the subsequent 9-month LMTB phase in which higher doses were given was <20 mg MT/kg/day (the lowest dose studied). Hematological toxicity was seen in minipigs even at the lowest dose studied; therefore, the NOAEL is considered to be <3 mg MT/kg/day. The hematological effects in rats occur at exposures that are 2.1-fold higher than in humans at an LMTM dose of 16 mg/day and in minipigs at exposures that are 1.2-fold higher. In rats and minipigs (but not monkeys) at the hematologically toxic doses, myeloid generation is also affected, and extramedullary hematopoiesis is seen. Pigment (hemosiderin) deposition becomes evident in liver and renal cortical tubules (some lipofuscin is also present in minipigs) with no adverse effect on either liver or kidney function evident. At relatively high doses, effects on white blood cells (WBCs) are seen, but not consistently across species (seen only in rats, not monkeys or minipigs). Decreases in circulating neutrophils occurred with an exposure-based safety margin of 8.9.

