 While remote administration of the ADAS-cog13, MMSE, CDR, and ADCS-ADL23 has not been validated, MedAvante ProPhase will prepare written instructions for the rater that detail how to alter administration of each of the scales in order to minimize any impact on the data collected, and to minimize loss of data.

- In subjects with CDR 0.5 at Screening, F-FDG-PET imaging will be performed at Baseline (unless the Sponsor approves subject randomization without a brain F-FDG-PET scan, if the scan cannot be performed due to COVID-19). All F-FDG-PET scans are to be performed at approved PET centers using approved scanners; no alternative scanners will be accepted and there is to be no change in scanner for a given subject over the course of the study.
  - If a Baseline F-FDG-PET scan cannot be done due to lack of imaging facility, a follow-up F-FDG-PET scan will not be required
- Blood samples for safety laboratory assessments and PK as well as optional genotyping may be collected from subjects in the clinic at the site, in the subject's home, or at other safe, suitable alternative location, using the central laboratory (Labcorp) kits for sample collection; samples are to be shipped to Labcorp for analysis using a designated courier service, and the shipment parameters as per the laboratory manual must be adhered to during transfer (e.g., between the subject's home, primary care provider, or clinical site).
  - If blood samples for safety laboratory assessments cannot be shipped to Labcorp, sample analysis for hematology testing will be performed at a local laboratory. As the first post-Baseline (Visit 3) hematology sample analysis is key in monitoring the adverse event of special interest (AESI) of hemolytic anemia, clinical sites will not be permitted to randomize a subject if the Visit 3 blood collection plan is not in place. Blood chemistry and genotyping samples can also be analyzed at a local laboratory or may be stored at -20 °C at the clinical site until shipment to the central laboratory.

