## 2.3. Double-Blind Treatment Phase (Week 0 up to Week 52)

Five post-Baseline visits are scheduled during the double-blind treatment phase (Visit 3 (Week 4): safety, and Visits 4, 5, 6, and 7 (Week 13, 26, 39, and 52): efficacy, imaging, and safety, see Table 2).

Unscheduled visits may occur as needed for assessment, or upon early termination. In addition, subjects are to be followed as needed for the resolution or stabilization of an AE, including following the last dose, consistent with the Investigator's medical judgement.

The Baseline value is defined as the last non-missing value prior to first dose of study drug or value obtained on the same day of the first dose of study drug. In case of pre- and post-dose assessments at the Baseline visit, the pre-dose value will be used as the Baseline assessment. If no assignment to pre-/post-dose is possible algorithmically, it will be treated as pre-dose unless specified otherwise during the Blinded Data Review Meeting (BDRM).

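### Screening G6PD is linked to hemoglobin only through the Week 52 change, so a G6PD-related fall that has recovered by then would not be tied to G6PD, and no model tests whether the drug effect depends on G6PD

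*SAP*

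**What the plan says.** SAP 5.12.3 (Laboratory Data) holds the only analyses in either document that relate G6PD to hemoglobin.

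- **Correlation.** Within each of the three arms, the Pearson correlation "between the G6PD value at Screening and the change in hemoglobin from Baseline up to Week 52 visit will be analyzed", with scatter plots. On missing values: "If the Week 52 visit value is not available, the last available on-treatment value will be used".
- **ANCOVA.** The outcome is again the change to Week 52. The model has the randomization strata plus "the hemoglobin Baseline value and the total duration of exposure (see Section 5.12.1) as covariates, and the treatment indicator". It has no G6PD term: "This will be performed in two G6PD subgroups", one at 60 to 80 percent of the laboratory's lower reference bound and one above 80 percent.

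Hemoglobin is also reported without reference to G6PD. The same section says that the "change from Baseline to each on study evaluation and to the last available on-treatment value will be summarized for each clinical laboratory parameter".

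Week 4 data exist for this purpose. SAP 2.3 states: "Five post-Baseline visits are scheduled during the double-blind treatment phase (Visit 3 (Week 4): safety". SAP Table 5 gives Week 4 its own safety window, days 2 to 67.

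**The concern.** Hemolytic anemia is one of the two prespecified events of special interest (Protocol 16.11), and subjects with G6PD deficiency are excluded (Protocol 11.2, criterion 11). The sponsor has chosen to ask whether G6PD among eligible subjects relates to hemoglobin loss, but the planned answer rests on one late value per subject. If hemoglobin falls early and then recovers, the Week 52 change carries little or no trace of it.

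The second difficulty is the subgroup structure. Two separate ANCOVAs give two treatment estimates and no test that they differ. Whether the drug effect varies with G6PD is an interaction question.

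At stake is how a null result would be read. It could be taken as showing that G6PD does not matter within the eligible range, when the analysis was not aimed at the period in which an effect might appear.

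**Working it through.** The plan states no sample size, power or alpha for this analysis, so there is no figure to reproduce. Steps 1 to 3 compare the texts. Steps 4 and 5 are illustrations.

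**1. Which hemoglobin value is used.** One per subject: Week 52, else the last on-treatment value. There is no Week 4, lowest-value or repeated-measures version.

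**2. Whether another output makes the G6PD link.**

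| Output | Shows an early fall? | Split by G6PD? |
|---|---|---|
| By-visit summaries, shift tables, hemoglobin plots (SAP 5.12.3) | Yes, by arm | No |
| Any post-Baseline potentially clinically significant value, including a fall of 20% or more (SAP Table 6) | Yes, by arm | No |
| Related-parameter listings (SAP Table 7) | Yes, per subject | G6PD not listed |
| Special-interest-event table (SAP 5.12.2) | Yes, if reported as hemolytic anemia | No |
| Adverse event groupings by subgroup (SAP 5.12.2) | Yes, as anemia terms | G6PD not among the subgroups |

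**3. Who can bring a recovered value to Week 52.** A subject may recover on continued drug. A subject may also stop drug (Protocol 16.11.1 covers interruption and discontinuation for hemolysis) and keep to the assessment schedule, as Protocol 11.4.1 asks. The on-treatment fallback applies only when Week 52 is missing, so the second subject contributes an off-drug value. Exposure duration as a covariate does not bring back the early measurement.

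**4. Possible loss of signal (illustration).** The assumptions are a within-arm correlation r at Week 4, a fraction f of it gone by Week 52 so that the correlation there is r(1 − f), equal SDs at both visits, and two-sided 0.05. Arm size is 200 (Protocol 17.2), or 150 after the protocol's upper 25% withdrawal rate. With m = atanh(r) × √(n − 3), power = Φ(m − 1.960) + Φ(−m − 1.960).

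For n = 200, √197 = 14.036:
- r = 0.20: m = 0.2027 × 14.036 = 2.845, power 0.81.
- r = 0.10 (f = 0.50): m = 1.408, power 0.29.
- r = 0.05 (f = 0.75): m = 0.702, power 0.11.

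| n | Week 4 r | Power at Week 4 | f = 0.50 | f = 0.75 | f = 1 |
|---|---|---|---|---|---|
| 150 | 0.20 | 0.69 | 0.23 | 0.09 | 0.05 |
| 150 | 0.30 | 0.96 | 0.45 | 0.15 | 0.05 |
| 150 | 0.40 | >0.99 | 0.69 | 0.23 | 0.05 |
| 200 | 0.20 | 0.81 | 0.29 | 0.11 | 0.05 |
| 200 | 0.30 | 0.99 | 0.56 | 0.18 | 0.05 |
| 200 | 0.40 | >0.99 | 0.81 | 0.29 | 0.05 |

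**5. The low band.** Its size is not stated. Each subgroup ANCOVA estimates intercept 1, severity 2, region 1, prior use 1, baseline hemoglobin 1, exposure 1 and treatment 1 or 2, which is 8 or 9 parameters. If a share q of each 200-subject arm lies in the band, the difference between the two bands' treatment effects has SE = √(2/(200q) + 2/(200(1 − q))) in SD units. About 2.8 × SE is detectable with 80% power:

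| q | Per arm in band | SE | Detectable difference |
|---|---|---|---|
| 2% | 4 | 0.714 | 2.00 SD |
| 5% | 10 | 0.459 | 1.28 SD |
| 10% | 20 | 0.333 | 0.93 SD |

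A comparison of bands would therefore be imprecise even if it were tested, which favors continuous G6PD.

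**The case against.** The strongest reply is that hemolysis is not hidden. A reader might infer that an early fall would be missed altogether. The documents do not support that: step 2 shows that it would appear by arm in several outputs. Only the link to G6PD is absent.

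A reader might also infer that the protocol requires a Week 4 analysis from the sentence "As the first post-Baseline (Visit 3) hematology sample analysis is key in monitoring the adverse event of special interest (AESI) of hemolytic anemia". That sentence sits in Protocol 10.2.1, a COVID-19 section. It supports a rule about having a Visit 3 blood collection plan before randomization, it does not mention G6PD, and it sets no analysis timepoint. It shows only that the sponsor regards that sample as informative for hemolysis.

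Nor do the documents show that hemoglobin in patients falls by Week 4 and then recovers. The phrase "manifesting as methemoglobinemia and a regenerative hemolytic anemia" comes from the nonclinical section (Protocol 8.1.2). Recovery is a possibility that the analysis should allow for, not a documented pattern. Likewise, the documents exclude G6PD deficiency but do not say that eligible subjects with lower values are at higher risk.

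It is also fair that G6PD enters the correlations as a continuous value and that the arms can be compared by eye. SAP 4.1 reserves formal testing for primary and secondary efficacy endpoints, so this is a supportive safety analysis. These points limit the concern's weight. They do not supply a Week 4 version or an interaction term.

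**Conclusion.** The point stands as a gap in a supportive safety analysis, not as a failure to monitor hemolysis. As written, the analysis can detect a G6PD relation only to the extent that it persists in the Week 52 value, and it never tests whether the drug effect depends on G6PD. A null result should not be read as evidence that G6PD is irrelevant to early hemoglobin loss.

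The size cannot be fixed from the documents. Over the assumed range (Week 4 correlations of 0.2 to 0.4, 150 or 200 subjects per arm), power is 0.69 to above 0.99 at Week 4. It is 0.09 to 0.81 at Week 52 with half or three quarters of the association gone, and equals the alpha level with full recovery. The correlations, recovery fractions, equal SDs and low-band shares are all assumptions. The textual findings do not depend on them.

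**What to change.** Keep the Week 52 analysis as planned. SAP Section 10 records that version 3.0 followed the 28 April 2022 data snapshot and partial unblinding, so replacing the outcome now would be a post hoc change. Add the following, labelled as post hoc supplementary safety analyses:

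1. The same scatter plots and per-arm correlations for the change to Week 4 and, as a further outcome, for the lowest on-treatment hemoglobin minus Baseline. Use scheduled samples only. Unscheduled testing follows adverse events (Protocol 15.4 and 16.11.1), and the worst-value-per-window rule would otherwise let those draws in.
2. One model in all subjects with continuous screening G6PD, treatment and their interaction, keeping the planned strata and baseline hemoglobin.
3. Descriptive display of the 60 to 80 percent band if it is small.

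Before item 3, check the band against the exclusion. The band is relative to the lower reference bound, while the exclusion is below 60% of normal, given as 6.1 U/g. The bound is not stated. At 7.6 U/g, 80% of it is 6.08 and no eligible subject would fall in the band. At 6.1/0.6 = 10.17 U/g the band runs from 6.1 to 8.1. The two definitions need to be reconciled.

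The cost is a few more outputs and some programming on data already collected. The scheduled-visit minimum is noisier than a single visit and depends on how many visits a subject attends, so Week 4 is the cleaner of the two added outcomes.
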